8.3.2. Assessment of Adverse Events

- All AEs and SAEs whether volunteered by the subject, discovered by study personnel during questioning, or detected through physical examination, laboratory test, or other means will be reported appropriately.
- Each reported AE or SAE will be described by its duration (i.e., start and end dates), regulatory seriousness criteria if applicable, suspected relationship to the study treatment (see following guidance), and actions taken.
- To ensure consistency of AE and SAE causality assessments, investigators should apply the following general guideline:

- Yes
 - There is a plausible temporal relationship between the onset of the AE and administration of the study treatment, and the AE cannot be readily explained by the subject's clinical state, intercurrent illness, or concomitant therapies
- And/or
 - The AE follows a known pattern of response to the study treatment; and/or the AE abates or resolves upon discontinuation of the study treatment or dose reduction and, if applicable, reappears upon re-challenge.
- No
 - Evidence exists that the AE has an etiology other than the study treatment (e.g., preexisting medical condition, underlying disease, intercurrent illness, or concomitant medication):
- And/or
 - The AE has no plausible temporal relationship to study treatment administration (e.g., cancer diagnosed 2 days after first dose of study treatment).

Expected adverse events are those adverse events that are listed or characterized in the Package Insert or current Investigator Brochure.

Unexpected adverse events are those not listed in the Package Insert (P.I.) or current Investigator Brochure (I.B.) or not identified. This includes adverse events for which the specificity or severity is not consistent with the description in the P.I. or I.B. For example, under this definition, hepatic necrosis would be unexpected if the P.I. or I.B. only referred to elevated hepatic enzymes or hepatitis.

8.4. Procedures for eliciting, recording, and reporting adverse events

8.4.1. Overview

- Eliciting adverse events

A consistent methodology for eliciting AEs at all subject evaluation time points should be adopted. Examples of non-directive questions include:

- "How have you felt since your last clinical visit?"
- "Have you had any new or changed health problems since you were last here?"

- Specific Instructions for Recording Adverse Events

Investigators should use correct medical terminology/concepts when reporting AEs or SAEs. Avoid colloquialisms and abbreviations.

8.4.2. Diagnosis vs. Signs and Symptoms

If known at the time of reporting, a diagnosis should be reported rather than individual signs and symptoms (e.g., record only liver failure or hepatitis rather than jaundice, asterixis, and elevated transaminases). However, if a constellation of signs and/or symptoms cannot be medically characterized as a single diagnosis or syndrome at the time of reporting, it is ok to report the information that is currently available. If a diagnosis is subsequently established, it should be reported as follow-up information.

8.4.3. Deaths

All deaths that occur during the protocol-specified AE reporting period, regardless of attribution, will be reported to the appropriate parties. When recording a death, the event or condition that caused or contributed to the fatal outcome should be reported as the single medical concept. If the cause of death is unknown and cannot be ascertained at the time of reporting, report “Unexplained Death”.

8.4.4. Preexisting Medical Conditions

A preexisting medical condition is one that is present at the start of the study. Such conditions should be reported as medical and surgical history. A preexisting medical condition should be re-assessed throughout the trial and reported as an AE or SAE only if the frequency, severity, or character of the condition worsens during the study. When reporting such events, it is important to convey the concept that the preexisting condition has changed by including applicable descriptors (e.g., “more frequent headaches”).

8.4.5. Hospitalizations for Medical or Surgical Procedures

Any AE that results in hospitalization or prolonged hospitalization should be documented and reported as an SAE. If a subject is hospitalized to undergo a medical or surgical procedure as a result of an AE, the event responsible for the procedure, not the procedure itself, should be reported as the SAE. For example, if a subject is hospitalized to undergo coronary bypass surgery, record the heart condition that necessitated the bypass as the SAE.

Hospitalizations for the following reasons do not require reporting:

- Hospitalization or prolonged hospitalization for diagnostic or elective surgical procedures for preexisting conditions
- Hospitalization or prolonged hospitalization required to allow efficacy measurement for the study or
- Hospitalization or prolonged hospitalization for scheduled therapy of the target disease of the study.

8.4.6. Pregnancy

If a female subject becomes pregnant while receiving investigational therapy or within 30 days after the last dose of a study treatment, a report should be completed and expeditiously submitted to the Coordinating Center who will submit report to Genentech, Inc. if study treatment is Lucentis. Follow-up to obtain the outcome of the pregnancy should also occur. Abortion, whether accidental, therapeutic, or spontaneous, should always be classified as serious, and expeditiously reported as an SAE. Similarly, any congenital anomaly/birth defect in a child born to a female subject exposed to a study treatment should be reported as an SAE.

8.4.7. Product complaints

A product complaint is any written or oral information received from a complainant that alleges deficiencies related to identity, quality, safety, strength, purity, reliability, durability, effectiveness or performance of a product after it has been released and distributed to the commercial market or clinical trial. Clinical centers are required to report product complaints for study treatments to the CC on an Unanticipated Event (UA) form within 7 days of learning of the event.

A recent FDA update to the Post Marketing Safety Reporting (PMSR) regulation requires the Marketing Authorization Holder (MAH) to report product complaints to the FDA. Genentech, the

MAH for ranibizumab (Lucentis), is donating the ranibizumab for U.S. clinical centers for the MERIT Trial. As part of the CC's agreement with Genentech, the CC will report any product complaints for ranibizumab reported for the MERIT Trial. The CC will report complaints to Genentech within 15 days

8.4.8. Post-Study Adverse Events

The investigator should expeditiously report any SAE occurring after a subject has completed or discontinued study participation if attributed to prior exposure to study treatment. If the investigator should become aware of the development of cancer or a congenital anomaly in a subsequently conceived offspring of a female subject who participated in the study, this should be reported as an SAE.

8.4.9. Reconciliation

The Coordinating Center (the sponsor) agrees to conduct reconciliation for the product donated by Genentech (i.e., Lucentis). The Coordinating Center will agree to the reconciliation periodicity and format, but agree at minimum to exchange quarterly line listings of cases received by the other party. If discrepancies are identified, the Coordinating Center and Genentech will cooperate in resolving the discrepancies. The responsible individuals for each party shall handle the matter on a case-by-case basis until satisfactory resolution.

8.4.10. AEs of Special Interest (AESIs)

AEs of Special Interest are defined as a potential safety problem, identified as a result of safety monitoring of the Product.

The Lucentis Events of Special Interest are:

- Retinal pigment epithelial tear
- Increased intraocular pressure to > 30mm Hg not responsive to maximal topical IOP-lowering drugs measured on 2 separate days
- Traumatic cataract
- Endophthalmitis
- Intraocular inflammation of greater than 2+ cells (including vitritis and uveitis)
- Retinal detachment
- ATEs, including stroke

8.4.11. SAE Reporting

Investigators must report all SAEs to the Coordinating Center who will report events as applicable to Genentech within the timelines described below. The completed Medwatch/case report should be faxed immediately upon completion to Genentech Drug Safety at:

- Relevant follow-up information should be submitted to the Coordinating Center who will submit to Genentech Drug Safety as soon as it becomes available.
- Serious AE reports that are related to the Lucentis and AEs of Special Interest (regardless of causality) will be transmitted to the Coordinating Center within three (3) calendar days of the Awareness Date, The Coordinating Center will transmit Genentech within fifteen (15) calendar days of the Awareness Date.
- Serious AE reports that are unrelated to the Lucentis will be transmitted to the Coordinating Center within three (3) days of the Awareness Date. The Coordinating

Center will submit these reports to Genentech within thirty (30) calendar days of the Awareness Date.

- Additional Reporting Requirements to Genentech include the following:
- Any reports of pregnancy following the start of administration with the Lucentis will be transmitted to the Coordinating Center within seven (7) days of the Awareness date. The Coordinating Center will submit the report to Genentech within thirty (30) calendar days of the Awareness Date.
- The Coordinating Center will forward all Non-serious Adverse Events originating from the Study in a quarterly report or a final listing with the final safety report (FSR) to Genentech.

Note: Investigators should also report events to their IRB as required.

8.4.12. CC event reporting to Genentech

The CC will report all protocol-defined AEs, SAEs, AE of special interest, Special Situation Reports (including pregnancy reports) and Product Complaints with an AE for participants randomized to or who received ranibizumab during the trial to Genentech by [contact] or email: [contact].

The CC will report ranibizumab Product Complaints without an AE to Genentech by email: [contact]

8.5. MedWatch 3500A Reporting Guidelines

The Coordinating Center is responsible for the following.

In addition to completing appropriate patient demographic and suspect medication information, the report should include the following information within the Event Description (section 5) of the MedWatch 3500A form:

- Protocol description (and number, if assigned)
- Description of event, severity, treatment, and outcome if known
- Supportive laboratory results and diagnostics
- Investigator's assessment of the relationship of the adverse event to each investigational product and suspect medication

Follow-up Information

Additional information may be added to a previously submitted report by any of the following methods:

- Adding to the original MedWatch 3500A report and submitting it as follow-up
- Adding supplemental summary information and submitting it as follow-up with the original MedWatch 3500A form
- Summarizing new information and faxing it with a cover letter including patient identifiers (i.e. D.O.B. initial, patient number), protocol description and number, if assigned, brief adverse event description, and notation that additional or follow-up information is being submitted (The patient identifiers are important so that the new information is added to the correct initial report)

Occasionally Genentech may contact the reporter for additional information, clarification, or current status of the patient for whom and adverse event was reported. For questions regarding

SAE reporting, you may contact the Genentech Drug Safety representative noted above or the MSL assigned to the study. Relevant follow-up information should be submitted to Genentech Drug Safety as soon as it becomes available and/or upon request.

MedWatch 3500A (Mandatory Reporting) form is available at <http://www.fda.gov/medwatch/getforms.html>

8.6. Additional Reporting Requirements for IND Holders

The Coordinating Center holds the IND for MERIT and is responsible for the following.

For Investigator-Sponsored IND Studies, some additional reporting requirements for the FDA apply in accordance with the guidance set forth in 21 CFR § 600.80.

Events meeting the following criteria need to be submitted to the Food and Drug Administration (FDA) as expedited IND Safety Reports according to the following guidance and timelines:

7 Calendar Day Telephone or Fax Report:

The Investigator is required to notify the FDA of any fatal or life-threatening adverse event that is unexpected and assessed by the investigator to be possibly related to the use of a study treatment. An unexpected adverse event is one that is not already described in the study treatment Investigator Brochure. Such reports are to be telephoned or faxed to the FDA and Genentech within 7 calendar days of first learning of the event.

15 Calendar Day Written Report

The Investigator is also required to notify the FDA and all participating investigators, in a written IND Safety Report, of any serious, unexpected AE that is considered reasonably or possibly related to the use of a study treatment. An unexpected adverse event is one that is not already described in the study treatment investigator brochure.

Written IND Safety reports should include an Analysis of Similar Events in accordance with regulation 21 CFR § 312.32. All safety reports previously filed by the investigator with the IND concerning similar events should be analyzed and the significance of the new report in light of the previous, similar reports commented on.

Written IND safety reports with Analysis of Similar Events are to be submitted to the FDA, Genentech, and all participating investigators within 15 calendar days of first learning of the event. The FDA prefers these reports on a Medwatch 3500 form, but alternative formats are acceptable (e.g., summary letter).

FDA fax number for IND Safety Reports:

Fax: [name]

All written IND Safety Reports submitted to the FDA by the Investigator must also be faxed to Genentech Drug Safety:

[contact] or [contact]

*And to the Site IRB**For questions related to safety reporting, please contact Genentech Drug Safety:*

[contact]

[contact] or [contact]

*IND Annual Reports**Copies to Genentech:*

All IND annual reports submitted to the FDA by the Sponsor-Investigator should be copied to Genentech. Copies of such reports should be faxed to Genentech Drug Safety:

[contact] or [contact]

8.7. Study Close-Out**The Coordinating Center is responsible for the following.**

Any study report submitted to the FDA by the Sponsor-Investigator should be copied to Genentech. This includes all IND annual reports and the Clinical Study Report (final study report). Additionally, any literature articles that are a result of the study should be sent to

Genentech. Copies of such reports should be mailed to the assigned Clinical Operations contact for the study:

E-mail: [contact]

[contact]

9. Sample size and statistical methods

9.1. Sample size, power and detectable differences

The study is powered to test whether intravitreal methotrexate and ranibizumab are each superior to intravitreal dexamethasone in terms of change in central subfield thickness. A Bonferroni correction is used to adjust for the co-primary hypotheses, i.e. a two-sided type I error rate of $0.05/2 = 0.025$ will be used to determine statistical significance. The primary outcome, retinal thickness, is measured on the log-scale, which translates to an assessment of relative change compared to baseline. The expected percent reduction in retinal thickness from baseline for dexamethasone is 25% ($\log [0.75] = -0.2877$); macular edema that persists after corticosteroid treatment is expected to be less likely to benefit from additional corticosteroid therapy. We expect the novel treatment arms to produce a reduction of 38% ($\log [0.62] = -0.4780$). A sample size of 79 independent eyes per treatment group, i.e. 79 individuals with one eye for each individual, will provide 91% power to demonstrate an improvement in the percent reduction in retinal thickness from 25% to 38% with a two-sided type I error rate of 0.025. Assuming a between-eye correlation of 0.4, 25% bilateral disease, and a 10% loss to follow-up, we need to enroll 80 individuals in each treatment arm (240 total), 8 fewer participants per arm than would be required if only one eye was included for individuals with bilateral disease after adjusting for loss to follow-up.

We also will compare the percent change in retinal thickness for intravitreal injections of methotrexate and ranibizumab; however, the percent change is expected to be similar for these therapies and the study is not powered to detect equivalence. The calculation presented here is meant to demonstrate the type of difference that would be detectable with the sample required for the primary hypotheses. As noted above, we assume that the reference group will have a percent reduction of 38% ($\log [0.62]$) with a standard deviation for the change in log-retinal thickness of 0.33. A sample size of 79 independent eyes per treatment group (the equivalent of 80 individuals per arm assuming 10% loss to follow-up, 25% bilateral disease and between-eye correlation of 0.4) provides 80% power to detect a difference between the reference percent change of 38% and a percent change of 46.6% ($\log [0.534]$) with a two-sided type I error rate of 0.05.

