The rates of adverse events will be compared using a Negative Binomial model with a random effect for individual. The overall burden and timing of serious adverse events will be displayed graphically by plotting a single line for each individual highlighting the start and stop dates of SAE sorted by the time of first event¹³³. Robust standard errors will be computed for all analyses using statistical program-based approaches or the bootstrap, where the unit of analysis is the individual. In addition, the models will be adjusted for the stratification variable used during randomization (presence or absence of concomitant systemic corticosteroid and/or immunosuppressive therapy). All primary analyses will be according to treatment assignment (i.e. following the principles of Intention to Treat). A sensitivity analysis of based upon treatment received will be performed for comparison. Additional sensitivity analyses will be performed to assess the impact of missing data. These include 'best' and 'worst' case single imputations as well as multiple imputation and pattern mixture approaches^{134, 135}.

10. Efficacy monitoring and stopping guidelines

The guidelines for the interim efficacy analyses were developed by the Data and Safety Monitoring Committee (DSMC) and MUST Executive Committee. Additional unplanned efficacy analyses will be done if recommended by the DSMC or MUST Executive Committee.

A single pre-planned interim efficacy analysis will be performed once 40% of participants have completed the 12-week visit (the primary outcome time-point). The type I error for each of the co-primary comparisons is 0.025, i.e. half was allocated to each comparison to control the study wide type I error rate. For each comparison, the type I error thresholds would be 0.00016 at the interim analysis and 0.02484 at the final analysis to maintain a global 0.025 error rate over the course of the trial based upon O'Brien-Fleming boundaries.

11. Regulatory and ethical issues

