Trial monitoring will be conducted by a study Data and Safety Monitoring Committee (DSMC). The DSMC consists mostly of members of the standing DSMC which monitored the Multicenter Uveitis Steroid Treatment (MUST) Trial and now is monitoring the MUST Follow-up Study. The Chair of the MUST DSMC, who is a biostatistician, is unable to serve because of potential conflicts of interest. Hence a new member who is an experienced methodologist for ophthalmic studies was appointed and the Chair of the DSMC for this protocol is one of the clinical experts. The committee consists of voting members with expertise in biostatistics, clinical trial design, and ophthalmology who were appointed by NEI and non-voting members (i.e., Study Officers).

For each DSMC meeting, data will be summarized by personnel from the CC and presented to the DSMC. The DSMC will meet at least twice a year (one in-person meeting and one meeting by conference call). Additional meetings/conference calls may be requested by DSMC Chair and/or NEI Project Officer. Meeting reports will include information summaries related to monitoring the safety and effectiveness of the study treatments as well as study performance including data quality and clinic performance. Pertinent information from outside sources such as a reprint of a recent publication reporting on results of other, related studies will also be included as available. All reports will include tables and graphs that summarize and formally compare baseline and adverse event data by treatment assignment, and if indicated, within specific subgroups. A single interim efficacy analysis formally comparing the treatment groups will be performed once 50% of participants have completed the 12-week visit (See Section 10). Graphical and/or numeric summaries (without formal statistical comparisons) will be provided in the meeting books that are not associated with the interim efficacy analysis. Additional efficacy analyses may be performed at the request of the DSMC if necessary.

The DSMC Medical Safety Officer, appointed from among the physician voting members of the DSMC, will review all SAE reports received by the CC as described in section 5.1.

12. References

Bibliography

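### Optional improvement: a Holm step-down in place of fixed Bonferroni keeps the 0.05 family-wise error and raises the power to show both drugs superior from about 86% to 91%

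*Combined protocol and SAP*

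**What the plan says.** Section 9.1 sets the aim: "The study is powered to test whether intravitreal methotrexate and ranibizumab are each superior to intravitreal dexamethasone". It then says that "A Bonferroni correction is used to adjust for the co-primary hypotheses" and gives 91% power for each comparison "with a two-sided type I error rate of 0.025". Section 10 (Efficacy monitoring and stopping guidelines) repeats the split, explaining that "half was allocated to each comparison to control the study wide type I error rate", and sets thresholds of 0.00016 at a single interim and 0.02484 at the final analysis for each comparison.

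Neither section mentions a step-down rule. No power is given for showing both drugs superior, and nothing in the plan requires both to succeed.

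Two places leave room for further looks without allocating error to them. Section 10 says "Additional unplanned efficacy analyses will be done if recommended by the DSMC or MUST Executive Committee", and Section 11.2 (Data and safety monitoring) says "Additional efficacy analyses may be performed at the request of the DSMC if necessary".

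**The concern.** The only reason the plan gives for holding each comparison at 0.025 is control of the study-wide error, and Holm gives the same control. Suppose one drug is shown superior and the other ends with a final p-value between 0.02484 and 0.04984. The plan must then call the second drug non-significant, although its own study-wide 0.05 would allow the claim. Power is lost for no gain on the plan's own criterion.

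A smaller point concerns reporting. The trial asks about each of two drugs, and a reader may take 91% as the chance of a positive answer on both. That chance is lower and is not stated.

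**Working it through.** **Inputs (Section 9.1 unless noted).** Reduction of 25% with dexamethasone, log(0.75) = −0.2877; reduction of 38% in each novel arm, log(0.62) = −0.4780; 79 independent eyes per arm. The SD of the change in log thickness is 0.33. It is stated only for the methotrexate–ranibizumab comparison, but it also reproduces the primary power. Allocation is 1:1:1 (Section 3.1), so with equal variances the two test statistics correlate 0.5 through the shared dexamethasone arm. The interim is at 40%, with thresholds 0.00016 and 0.02484 (Section 10).

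**The plan's own figure.** The difference is 0.4780 − 0.2877 ≈ 0.1904. Its standard error is 0.33 × √(2/79) = 0.0525, so each test statistic has mean 0.1904/0.0525 = 3.63. At two-sided 0.025 the power is 91.7% (normal) or 91.2% (noncentral t), against 91% stated. The effective sample size also agrees: 80 × 0.9 × (0.75 + 0.25 × 2/1.4) = 79.7, against 79.

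**Why Holm is valid here.** By closed testing:
- The joint null is tested exactly as now: 2 × (0.00016 + 0.02484) = 0.05.
- Each single null is tested at 0.00016 at the interim and 0.04984 at the final, which sum to 0.05.

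The family-wise error is therefore at most 0.05 whatever the correlation, and every Bonferroni rejection is kept.

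**Power, single look (bivariate normal, mean 3.63, correlation 0.5).**
- Bonferroni, both: P(both p ≤ 0.025) = 85.9%.
- Holm, both: P(smaller p ≤ 0.025 and larger p ≤ 0.05) = 91.3%.

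**Power and error with the 40% interim.** These were simulated two-sided with millions of replicates. Holm adds 0.04984 at the final for the other comparison once one is rejected, and the trial is assumed to continue after one comparison crosses.

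| Scenario and quantity | Bonferroni | Holm |
|---|---|---|
| 38% and 38%: power per drug | 91.7% | 94.4% |
| 38% and 38%: both significant | 85.8% | 91.2% |
| 38% and 38%: at least one significant | 97.5% | 97.5% |
| 38% and 25%: error on the ineffective drug | 2.5% | 4.6% |
| Other drug always rejected: error on the ineffective drug | 2.5% | 5.0% |
| 25% and 25%: family-wise error | 4.6% | 4.6% |

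**Sensitivity (both significant, Bonferroni to Holm).**
- Single look: SD 0.30, 92.8% to 96.0%; SD 0.36, 77.3% to 84.8%; SD 0.40, 65.1% to 74.7%. Ignoring the shared-control correlation, 84.1% to 90.5%.
- With the interim: Section 10 does not say whether the trial continues if only one comparison crosses. At the planned effects the chance of any interim crossing is 11.9%. If everything stopped at the first crossing, power for both would be 76.1% to 81.4%.
- Assumed unequal effects of 38% and 35% (an illustration, not from the plan): weaker drug 68.5% to about 76.7%; both 65.9% to about 75.5%.

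**Unallocated looks.** Assume one unplanned look at 70% information, tested at 0.02484 with no allocation. The error on one true null is then 3.9% with a final threshold of 0.02484 and 5.9% with a recycled 0.04984. Extra looks inflate the error under either rule, but under Holm they can take it above 5%.

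**The case against.** The strongest reply is that nothing is broken. Bonferroni is stated consistently, holds the error for each drug at 2.5% and goes with simple 97.5% intervals. The plan does not seek joint success, and power for at least one drug does not change. If only one drug works, its power moves only from 91.7% to 91.8%, while the false-positive chance for the other rises to 4.6%. All of this is true. It makes the change optional. It does not remove the benefit, because the plan's stated criterion is the study-wide error and Holm respects it.

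The second reply is that it may be too late. The revision history runs to version 1.8 of August 2020, and the documents do not say whether the interim has taken place. Section 10 puts the interim at 40% of participants and Section 11.2 still says 50%. Section 11.2 also lets DSMC meeting books carry graphical or numeric summaries outside the interim, without saying that they are pooled over arms. This stands as a limit on when the change may be made: by-arm effectiveness summaries count as comparative results just as the interim does.

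Third, a two-sided trigger would let a drug significantly worse than dexamethasone release the larger level for the other. Error control still holds, but the text should say which trigger is meant.

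**Conclusion.** The point holds as a low-cost, optional improvement; the existing plan is valid. Under the planned effects, SD 0.33, 79 effective eyes per arm and continuation after a single crossing, Holm adds about 5 points of power to show both drugs superior (85.8% to 91.2%) and about 3 points per drug (91.7% to 94.4%), with the family-wise error still at or below 0.05. The gain depends on both drugs working. The cost is a per-drug error that can rise from 2.5% towards 5%.

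The 91% for both under Holm happens to match the plan's 91% per comparison; they are different quantities. The missing power for both is a reporting remark only.

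**What to change.** First establish whether anyone who would decide on the change has seen comparative efficacy results, from the interim or from by-arm DSMC summaries.

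If none have been seen:
- In Section 9.1, name Holm as the procedure.
- In Section 10, keep 0.00016 and 0.02484 for each comparison. Add that once either comparison is rejected at either look, the other is tested at the final analysis at 0.05 − 0.00016 = 0.04984. Say whether rejection in either direction counts.
- State that 0.00016 and 0.04984 are a simple sum that leaves the interim rule unchanged, not an O'Brien-Fleming pair for 0.05. A true O'Brien-Fleming second step would change power by only 0.1 to 0.2 points.
- State that any additional efficacy look needs its own error allocation, and say whether the trial continues if one comparison crosses at the interim.

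If comparative results have been seen, keep Bonferroni.

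In either case, report the power for both hypotheses (about 86% with Bonferroni, about 91% with Holm if adopted) beside the per-comparison 91%.

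The cost is one sentence in Section 9.1 and a few in Section 10, with no patients and no data. It needs the agreement of the DSMC and the MUST Executive Committee, who developed the interim guidelines. Intervals that match Holm are less simple; 97.5% intervals can still be shown.
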